## 3 INVESTIGATIONAL PLAN

### 3.1 Overall Study Design and Plan

This study is designed to compare ORMD-0801 given QD versus TID in subjects with T1D. The study will consist of seven visits (including Screening Visit).

During Screening, subjects will be required to sign the informed consent form. Medical and medication history and demographic information will be collected. Eligibility for participation will be evaluated. Vital signs (height, weight, seated SBP/DBP, and heart rate) will be measured, physical examination will be performed, and a blood and urine sample will be collected for hematology/chemistry/urinalysis.

Eligible subjects will be scheduled to return to the clinic in 1 week (Visit 2). Subjects fulfilling all inclusion/exclusion criteria will have a CGM placed, provided with a diary, dispensed placebo capsules and asked to return to the clinic in 10 days (Visit 3, Day 1) for randomization. At Visit 3, data from CGM will be downloaded and diaries will be collected. Blood samples

will be collected in fasting for chemistry and HbA1C. Subjects will be randomized to receive either ORMD-0801 24 mg given once daily at bedtime, or ORMD-0801 8 mg given three times a day, 45-90 minutes before meals. Subjects will be instructed to continue their normal diet, and to adjust their basal and bolus insulin in the normal fashion. Subjects will be instructed to return to the clinic in 10 days before Visit 5 (Visit 4, Day 18). At Visit 4, compliance will be assessed, IMP and diary dispensed and the CGM will be placed. Subjects will be instructed to return to the clinic in 10 days for Visit 5 (Day 28). At Visit 5 a blood sample for chemistry panel and HbA1C will be drawn, the diary collected, the CGM removed and the patient will be crossed over to the alternate treatment regimen. IMP will be dispensed, and the subject will be asked to return in 10 days before Visit 7 for Visit 6 (Day 46). At Visit 6, compliance will be checked, IMP and a diary will be dispensed and the CGM will be placed. Subjects will be instructed to return in 10 days for Visit 7 (Day 56). At Visit 7 the CGM will be removed, the diary will be collected, compliance checked, blood sample will be drawn for a chemistry panel and HbA1C. A physical examination will be performed, and the subject will exit the study.

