**Table 1 Footnotes**

Vital signs include height, weight, heart rate, SBP, and DBP. Height will be measured at Screening only, without shoes.

CGM monitor applied at Visits 2, 4, and 6; removed and downloaded at visits 3, 5, and 7 (or EW if applicable).

Diary dispensed at Visits 2, 4, and 6; collected and reviewed at visits 3, 5, and 7 (or EW if applicable).

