### 8.2 Statistical Considerations

Subjects will be analyzed under 3 treatment regimens: Standard of Care (Baseline), Once a Day Dosing (QD) and Three Times a Day Dosing (TID).

Information collected in the daily diaries or via the Continuous Glucose Monitor (CGM) on the final 10 days of treatment will be analyzed using a Repeated Measures Analysis of Covariance with subject as a random effect with each of the 10 days being a single measure. When analyzing the exogenous insulin variables, CGM parameters (mean 24 hour glucose value and 24 hour time within 70-180 mg/dL range) and patient reported carbohydrate intake will be included as covariates. When analyzing CGM parameters, exogenous insulin (basal and bolus insulin amounts) and patient reported carbohydrate intake will be included as covariates. Treatment least squares means and change from baseline estimates will be derived using this linear model.

Information collected at the day 28 visits will be analyzed using an Analysis of Covariance model with subject as a random effect. Treatment least squares means and change from baseline estimates will be derived using this linear model.

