2.8.1. Statistical Considerations

Subjects will be analyzed under 3 treatment regimens: Standard of Care (Baseline), Once a Day Dosing (QD) and Three Times a Day Dosing (TID).

Information collected in the daily diaries or via the Continuous Glucose Monitor (CGM) on the final 10 days of treatment will be analyzed using a Repeated Measures Analysis of Covariance with subject as a random effect with each of the 10 days being a single measurement. When analyzing the exogenous insulin variables, the CGM parameters (mean 24 hour glucose value and 24 hour time within 70-180 mg/dL range) and the patient reported carbohydrate intake will be included as covariates. When analyzing CGM parameters, the exogenous insulin (basal and bolus insulin amounts) and patient reported carbohydrate intake will be included as covariates. Treatment least squares means and change from baseline estimates will be derived using this linear model.

Information collected at the day 28 visits (Day 28 and Day 56) will be analyzed using an Analysis of Covariance model with subject as a random effect. Treatment least squares means and change from baseline estimates will be derived using this linear model.

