2.8.2. Basal, Bolus and Total Exogenous Insulin

The amount of basal, bolus and total exogenous insulin will be analyzed using the Repeated Measures Analysis of Covariance model indicated in Section 2.8.1. Least squares mean, standard error and 95% confidence intervals will be presented for each treatment regimen and changes between treatment regimens.

Total daily non-oral insulin requirements in units per kilogram (kg) body weight will also be analyzed in a fashion similar to basal, bolus and total exogenous insulin.

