2.8.3. Continuous Glucose Monitoring

Continuous Glucose Monitoring (CGM) will be summarized using 3 different time intervals:

- Daytime (6AM to 10PM),
- Nighttime (10PM to 6AM) and
- 24 Hour (6AM to 6AM).

The area under the curve (AUC) will be derived for each of the time periods for each of the 10 days for each treatment regimen. The average glucose measurement will be derived by dividing the AUC by the number of observed hours.

In addition to the mean values, the following CGM parameters will be derived for each time interval:

- Time that Glucose Value is Between 70 and 180,
- Time that Glucose Value is Less Than 70,
- Time that Glucose Value is Greater Than 180,

- Time that Glucose Value is Greater Than 250,
- Low Blood Glucose Index, and
- Glucose below 70 mg/dL Area Over the Curve (AOC₇₀)

All of the CGM parameters will be analyzed for each of the time periods (24-hour, daytime and nighttime) using the Repeated Measures Analysis of Covariance Model indicated in section 2.8.1.

Individual and mean figures will be generated to present the glucose curves / data for the 24-hour, daytime and nighttime measurements.

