2.11. Sample Size and Power Considerations

An estimated total of approximately 26 subjects are planned to be randomized to participate in the two dosing conditions in a randomized order. The study objectives (primary and secondary) have not been previously explored, so there are no estimates of means or standard deviations to perform power calculations.

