2.15. Computer Systems and Packages Used for Statistical Analyses

Server SAS® version 9.4 on the Microsoft Windows Server 2008R2 64-bit platform will be used for all analyses. All computations will be performed using SAS®. The exact form of the various algorithms will be the SAS® defaults. The output from any SAS® procedure will be used in the tables using SAS® macros.

3. Data Listing Shells

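### The day-level model for the primary endpoints has subject as its only named random term, so positive correlation between days within a period would make the QD-TID 95% confidence intervals too narrow

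*SAP*

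**What the plan says.** SAP 2.8.1 puts each subject under three regimens (baseline standard of care, QD, TID) and analyses daily diary and CGM values with a "Repeated Measures Analysis of Covariance with subject as a random effect with each of the 10 days being a single measurement". Protocol 8.2 has the same model: "Repeated Measures Analysis of Covariance with subject as a random effect with each of the 10 days being a single measure". The opening of Protocol section 8 leaves further detail to the SAP, but the SAP adds nothing on covariance.

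The insulin model has same-day CGM measures and carbohydrate intake as covariates. The CGM model has basal insulin, bolus insulin and carbohydrate intake.

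For insulin, SAP 2.8.2 states: "Least squares mean, standard error and 95% confidence intervals will be presented for each treatment regimen and changes between treatment regimens". For glucose, SAP 2.8.3 refers back to the same model: "All of the CGM parameters will be analyzed for each of the time periods (24-hour, daytime and nighttime) using the Repeated Measures Analysis".

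On software, SAP 2.15 falls back on SAS defaults, in the sentence that begins "The exact form of the various algorithms will be the". On variability, SAP 2.11 says that "there are no estimates of means or standard deviations to perform power calculations".

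**The concern.** Subjects are randomised once to a sequence at Visit 3 and cross over once at Visit 5 (Protocol 3.4 and 3.6). The experimental unit for the QD-TID comparison is therefore the subject's period, and the ten days are repeated readings within that unit. A random subject effect removes only what is constant for a subject across all three regimens. Anything particular to one subject in one period stays in the QD-TID difference and does not average out over ten days, but the model as written has no term for it.

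The design makes such variation plausible. Subjects are told to "adjust their basal and bolus insulin in the normal fashion", so a dose level reached in one period can persist through its ten days. Each period's glucose data also come from one sensor placement: "CGM monitor applied at Visits 2, 4, and 6; removed and downloaded at visits 3, 5, and 7".

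The plan has no efficacy test, success rule or power calculation. The standard errors and intervals of SAP 2.8.2 are thus the main evidence on the insulin primary endpoint. Intervals that are too narrow would make a chance difference between regimens look established. The same applies to any standard error taken from this model for mean 24-hour glucose, the other primary endpoint, and for the CGM secondary parameters.

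**Working it through.** The plan gives no power, effect size or SD, so it has no figure of its own to reproduce. The check is the actual coverage of the nominal 95% interval.

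**Inputs from the documents.** 3 regimens and 10 days per regimen (SAP 2.8.1); 24 subjects (Protocol 8.1) or about 26 (SAP 2.11); 95% intervals (SAP 2.8.2).

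**Assumed.** r = subject-by-period variance / daily residual variance, from 0 to 0.5. Balanced, complete data. No covariates at first.

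**Degrees of freedom**
- Day-level residual: 30n - n - 2, which is 720 - 24 - 2 = 694 at n = 24 and 780 - 26 - 2 = 752 at n = 26.
- Subject-by-regimen stratum: 2(n - 1), which is 46 at n = 24 and 50 at n = 26.

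**Variance of the QD-TID difference** (daily residual variance = 1)
- True: 2(r + 1/10)/n = 2(1 + 10r)/(10n).
- Model: 2 × MSE/(10n). The pooled residual has about 29 df per subject. Of these, 2 belong to the subject-by-regimen stratum, with expected mean square 1 + 10r. Hence MSE is about 1 + 20r/29.
- Ratio true/model = (1 + 10r)/(1 + 20r/29).
- Coverage = 2Φ(t / √ratio) - 1, where t is the 0.975 quantile on the day-level df (about 1.963).

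Example, r = 0.10: ratio = 2/1.069 = 1.87; √1.87 = 1.37; 1.963/1.37 = 1.43; coverage 85%.

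| r | True SE / model SE | Coverage, formula | Coverage, simulated, n = 24 | Coverage, simulated, n = 26 |
|---|---|---|---|---|
| 0 | 1.00 | 95% | 94.5% | 95.1% |
| 0.05 | 1.20 | 90% | 89.6% | 89.8% |
| 0.10 | 1.37 | 85% | 84.4% | 84.8% |
| 0.25 | 1.73 | 74% | 74.3% | 74.5% |
| 0.5 | 2.11 | 65% | 64.5% | 64.5% |

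The simulations used 6,000 replicates per cell.

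**Serial correlation alone.** AR(1) of 0.3 within a period gives coverage of about 85-86%, and 0.5 gives about 75-77%. A negative value errs the other way: AR(1) of -0.2 gives 98.2%.

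**With daily covariates** (n = 24, one or three covariates; assumed correlation with the outcome 0 to 0.8 at period level and 0 to 0.57 at daily level; covariate period/daily variance ratio set equal to r; no true regimen difference in outcome or covariates):

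| r | Coverage |
|---|---|
| 0.05 | 88-92% |
| 0.10 | 83-88% |
| 0.25 | 72-82% |
| 0.5 | 62-73% |

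The largest recovery is about 8 points (65% to 73% at r = 0.5). As a separate check, 300 REML fits per setting with one daily covariate were run at n = 26. When 10% of the variance beyond the subject effect was at period level (r = 0.11), the empirical SD of the estimate was 0.123 against a mean model SE of 0.086, with coverage 84%.

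**Using the correct stratum.** Analysis of 10-day means for all three regimens, without covariates, on 46 or 50 df gave coverage of 94.1-96.0% in every setting. If r = 0 the cost is the ratio of t quantiles: 2.009/1.963 = 1.02 at n = 26.

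**The case against.** The strongest reply is that the plan is silent rather than wrong. The term repeated measures, with the days named as the measurements, is compatible with a residual covariance still to be chosen. SAP 2.15 may refer to numerical algorithms and not to the covariance model. That reading is possible, but no structure is written anywhere, and subject is the only random term that is. If a structure is intended, stating it is the fix. If it is left open, the choice could be made after the data are seen, in an open-label study.

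Second, the size is unknown. This stands: nothing in the documents places the trial between 95% and 65% coverage, and at r = 0 the planned model is correct. The direction also needs positive correlation, which is the likelier case here. Negative correlation gives intervals that are too wide, which is wrong coverage as well.

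Third, the covariates may absorb more than the simulations show. This also stands: the 8-point figure belongs to the settings chosen and is not a bound. A covariate that followed the period-level drift closely would recover more. The covariates are measured on treatment and may themselves differ by regimen, so adjusted and unadjusted contrasts need not estimate the same quantity.

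Fourth, this is a small Phase 2 study with no pre-specified decision attached to the intervals, and SAP 2.8.3 does not restate intervals for CGM. Both facts are right. They limit the consequences but do not make the interval correct. With complete, balanced data and no covariates, the point estimates are unaffected.

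**Conclusion.** The concern holds as a conditional statement about the model as written. Under a subject-only random structure, positive correlation between days in the same period, beyond what the subject effect and covariates explain, makes the QD-TID intervals too narrow. Even a subject-by-period variance one tenth of the daily residual variance lowers coverage to about 85% without covariates (83-88% with the covariates simulated). The result is practically the same at 24 and 26 subjects.

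The omission and the algebra are certain. The amount of under-coverage in this trial is not, because every value of r and of the AR(1) correlation is assumed. Since the intervals are the plan's main evidence on the insulin primary endpoint and the protection costs almost nothing, this must be settled before the data are analysed.

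**What to change.** In SAP 2.8.1:

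- Add a random subject-by-regimen effect. It is the same as subject-by-period here, since each subject has each regimen in one period.
- Name a serial covariance for days within a period, such as AR(1), and use Kenward-Roger degrees of freedom.
- State that these choices override the SAS defaults of SAP 2.15 for this model.
- Keep the baseline regimen and the change-from-baseline estimates.
- Add a sensitivity analysis with one 10-day mean per subject and regimen, all three regimens, subject random. State whether covariates are omitted or entered as 10-day means. If they are omitted, the unit of analysis and the quantity estimated both change, so a discrepancy could not be put down to within-period correlation alone.

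A trial run of the proposed main model (REML, no covariates, n = 24, 250 runs per setting, t on 46 df in place of Kenward-Roger) gave coverage of 93-96% for r from 0 to 0.25.

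The cost is two sentences for the main model and one for the sensitivity analysis, with no new data. The intervals will be wider if within-period correlation is present, as they should be.

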1.3. Study Objectives

1.3.1 Primary Objectives

The primary objectives of the study are:

1. To compare the impact of Oral Insulin dosed QD to Oral Insulin dosed TID on exogenous basal and bolus insulin requirements in subjects with T1D during the last 10 days of each treatment period.
2. To compare the impact of Oral Insulin dosed QD to Oral Insulin dosed TID and associated adjustments of basal and bolus insulin on mean 24-hour glucose and parameters of glycemic variability as measured by a CGM over the last 10 days of each treatment period.

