2.8. Efficacy Evaluations

The primary endpoints for the study are:

1. To compare the amount of basal, bolus and total (basal + bolus) exogenous insulin utilized over the final 10 days of each treatment period.
2. To compare the impact of Oral Insulin dosed QD to Oral Insulin dosed TID and associated adjustments of basal and bolus insulin on mean 24-hour CGM glucose levels during the final 10 days of each treatment period.

The secondary endpoints for the study are:

1. Glucodynamics over the final 10 days of each treatment period as measured by CGM:
 - a. Time in range 70 – 180 mg/dL
 - b. Time <70 mg/dL
 - c. Time >180 mg/dL
 - d. Time >250 mg/dL
 - e. Glucose Coefficient of Variation
 - f. Low Blood Glucose Index (LBGI)
 - g. Glucose below 70 mg/dL Area Over the Curve (AOC₇₀)
2. Total daily non-oral insulin requirements in units per kilogram (kg) body weight over the last 10 days of each treatment period.

The exploratory endpoints for the study are:

1. HbA1c measured at the end of each treatment period
2. Patient diary-reported carbohydrate intake over the final 10 days of each treatment period
3. Changes in body weight from baseline (Visit 3) to the end of each treatment period
4. Other measures of hypoglycemia
 - a. Severe hypoglycemia events (impaired or loss of consciousness requiring assistance of another)
 - b. Documented symptomatic hypoglycemia (an event during which typical symptoms of hypoglycemia are accompanied by a measured plasma glucose concentration <70 mg/dL)
 - c. Total time <70 mg/dL by CGM
 - d. Nocturnal hypoglycemia, severe or documented symptomatic episodes (as defined above) occurring after the subject has retired for the primary sleeping period.

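### The only model contrast planned for primary endpoint 1, insulin used, adjusts for glucose, time in range and carbohydrate measured after randomisation, so it does not estimate the difference in insulin used

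*SAP*

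**What the plan says.** SAP 2.8 gives the first primary endpoint as "To compare the amount of basal, bolus and total (basal + bolus) exogenous insulin utilized over the final 10 days of each treatment period". Nothing there makes it conditional on glucose. The matching objective in SAP 1.3.1 uses a different noun: the impact of the two regimens "on exogenous basal and bolus insulin requirements in subjects with T1D during the last 10 days of each treatment period".

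For the analysis, SAP 2.8.2 states: "The amount of basal, bolus and total exogenous insulin will be analyzed using the Repeated Measures Analysis of Covariance model indicated in Section 2.8.1". That model is a repeated measures ANCOVA with subject as a random effect, "with each of the 10 days being a single measurement". SAP 2.8.1 names its covariates for insulin: "When analyzing the exogenous insulin variables, the CGM parameters (mean 24 hour glucose value and 24 hour time within 70-180 mg/dL range", followed by reported carbohydrate intake. Protocol 8.2 lists the same covariates: "When analyzing the exogenous insulin variables, CGM parameters (mean 24 hour glucose value and 24 hour time within 70-180 mg/dL range", again followed by carbohydrate. The LS means, standard errors, 95% CIs and differences between regimens all come from this model. Insulin per kg is handled in the same way. SAP 2.10 plans no other analyses.

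Protocol 3.1 tells subjects "to adjust their basal and bolus insulin in the normal fashion".

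**The concern.** Each covariate is an outcome of the same trial. In SAP 2.8, mean 24-hour glucose is primary endpoint 2, time in range is a secondary endpoint and carbohydrate intake is an exploratory one. All three are measured in the final 10 days of treatment, so the regimen can alter them.

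Glucose is also tied to the outcome in both directions. Subjects dose on their glucose: the protocol introduction describes type 1 doses as adjusted on self-monitored readings. A regimen that lowers glucose can therefore lower injected insulin by that route, and holding glucose fixed takes that part out. Injected insulin in turn lowers glucose, and the 6AM-6AM window of SAP 2.8.3 includes the night after most of the day's bolus doses. Conditioning on a result of the outcome distorts the comparison in its own right.

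At stake is the headline estimate and interval for the first primary endpoint. They could understate a real difference in insulin used, or show one where none exists.

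**Working it through.** **No plan figure to reproduce.** Protocol 8.1 and SAP 2.11 say that no means or standard deviations were available. Every effect size and SD below is therefore an assumption, chosen to show the mechanism and its range.

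**Algebra, glucose as a pathway only.** Let *d* be the direct effect of regimen on insulin (U/day), *D* the regimen's effect on glucose (mg/dL), and *k* the insulin response to glucose (U per mg/dL).

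- Contrast in insulin used = *d* + *kD*.
- Contrast adjusted for glucose = *d*. The part *kD* is lost.

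**Adding feedback.** Let *r* be the same-day effect of insulin on glucose (mg/dL per U).

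- Total contrast = (*d* + *kD*) / (1 - *kr*).
- Adjusted contrast = total contrast - *b* × (regimen difference in glucose), where *b* is the within-regimen slope of insulin on glucose. With feedback, *b* no longer equals *k*.

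**Simulation.** 26 subjects, 2 periods, 10 days per period, 1000 runs per row, within-subject least squares. Assumed daily SDs are 25 mg/dL for glucose and 5 U for insulin. The adjusted fit includes mean glucose and time in range; carbohydrate was left out. Contrasts are in U/day.

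| *d* | *D* | *k* | *r* | True total | Unadjusted | Adjusted |
|---|---|---|---|---|---|---|
| 0 | -15 | 0.10 | 0 | -1.50 | -1.51 | -0.01 |
| -2 | -15 | 0.10 | 0 | -3.50 | -3.51 | -2.01 |
| -3 | -10 | 0.05 | 0 | -3.50 | -3.50 | -3.01 |
| -3 | -20 | 0.15 | 0 | -6.00 | -6.00 | -2.99 |
| 0 | -15 | 0 | -1 | 0.00 | 0.00 | -0.59 |
| -3 | 0 | 0 | -1 | -3.00 | -3.02 | -2.90 |
| -3 | 0 | 0 | -2 | -3.00 | -3.00 | -2.58 |
| -3 | -10 | 0.10 | -1 | -3.64 | -3.64 | -3.27 |
| 0 | -15 | 0.10 | -1 | -1.36 | -1.36 | -0.58 |

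**Hand check of the fifth row.** Here insulin does not respond to glucose and the regimen has no effect on insulin. The within-regimen covariance of insulin and glucose is -1 × 5² = -25, and the variance of glucose is 25² + 5² = 650. So *b* = -25/650 = -0.0385. The adjusted contrast is 0 - (-0.0385 × -15) = -0.58, in line with the simulated -0.59.

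**Reading the table.** The unadjusted fit recovers the true total in every row, to within 0.02. In the four rows without feedback, the share lost to adjustment is 1.50/1.51 = 99%, 1.50/3.51 = 43%, 0.49/3.50 = 14% and 3.01/6.00 = 50%. In the feedback rows the adjusted figure equals neither the total nor the direct effect. For example, -0.58 is reported where the total is -1.36 and the direct effect is 0.

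**The case against.** **The objective says requirements.** A requirement can fairly be read as insulin needed at comparable glucose and intake, which is what these covariates seem to aim at, and both documents prespecify them. It stands that objective and endpoint use different words and that the SAP does not choose between them. It does not rescue the model. No section defines an equal-glucose target, and a covariate that insulin itself lowers would not deliver one, as the feedback rows show.

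**The loss may be small.** A reader might infer that the adjustment always wipes out the insulin effect. It does so only if the whole effect runs through glucose. The protocol introduction describes oral insulin acting in combination with injected insulin, so direct substitution cannot be excluded. Suppose a direct effect of -3 U/day and a glucose path of 0.2 to 1.2 U/day (slopes of 0.04 to 0.08 U per mg/dL times shifts of 5 to 15 mg/dL). Adjustment then removes 0.2/3.2 = 6% to 1.2/4.2 = 29%. This stands.

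**Basal may behave differently.** The documents do not say that basal dose follows the same day's glucose, so the sizes above should not be carried over to basal insulin.

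**The covariates might be period averages.** The SAP does not say. One record per day, and a CGM area derived "for each of the 10 days for each treatment regimen", make daily values the likelier reading. Either form is measured after randomisation.

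**Unadjusted insulin will be visible.** This is true: SAP 2.1 provides by-group descriptive statistics, SAP 4.1 a summary table of insulin usage, and SAP 4.3 figures of observed means. None is specified as a within-subject QD-TID contrast with a CI.

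**This is a small Phase 2 study.** It has no stated alpha, test or decision rule. That lowers the stakes of any single interval, but the estimate is still the main result for endpoint 1.

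**Conclusion.** The point holds. The planned QD-TID insulin contrast does not estimate the difference in insulin used, and it is not a clean requirement at equal control either. This rests on the documents' own text: the endpoint wording, the covariate list, the status of those covariates as endpoints, and the absence of any other model.

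The size cannot be computed from the documents. Under the assumed values it runs from a modest loss (-3.50 to -3.01 U/day) to a complete one (-1.51 to -0.01). With feedback, a non-zero contrast of -0.59 appears where the true total is zero. The documents do not support saying that the effect will vanish, or that the glucose-mediated part is exactly what is removed; exact removal needs glucose to be a pathway only. Nor do they support saying that the reader will see no unadjusted insulin data.

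**What to change.** In SAP 2.8.1-2.8.2 and Protocol 8.2-8.3:

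1. Take the primary QD-TID contrast and 95% CI for basal, bolus, total and U/kg insulin from a model with regimen and subject, without the CGM and carbohydrate covariates.
2. If a period term is added, code it as period 1 versus period 2 within the randomised periods. Baseline always comes first, so a three-level period factor would be aliased with the Baseline regimen.
3. Keep the covariate-adjusted model as supportive. Label it as insulin conditional on observed glucose and carbohydrate, not as a causal effect at equal control, and state whether the covariates are daily values or period means.
4. Align *utilized* in the endpoint with *requirements* in the objective, so that both name the same quantity.

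The cost is wording in two documents and one further model per insulin variable. No new data are needed.

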### 2.2 Endpoints

#### Primary Endpoints

1. To compare the amount of basal, bolus and total (basal + bolus) exogenous insulin utilized over the final 10 days of each treatment period.
2. To compare the impact of Oral Insulin dosed QD to Oral Insulin dosed TID and associated adjustments of basal and bolus insulin on mean 24-hour CGM glucose levels during the final 10 days of each treatment period.

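### The only CGM model for primary endpoint 2 holds injected insulin constant, although the endpoint asks for the QD-TID glucose effect together with the insulin adjustments

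*SAP*

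**What the plan says.** **The question.** SAP 2.8 defines primary endpoint 2 as a comparison of QD with TID and "associated adjustments of basal and bolus insulin on mean 24-hour CGM glucose levels during the final 10 days of each treatment period". Protocol 2.2 has the same text. Primary objective 2 (SAP 1.3.1) extends this to "associated adjustments of basal and bolus insulin on mean 24-hour glucose and parameters of glycemic variability".

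**The conduct.** Protocol 3.1 instructs subjects "to adjust their basal and bolus insulin in the normal fashion". The diary records basal and bolus insulin over the same 10-day windows as the CGM.

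**The model.** SAP 2.8.1 specifies a repeated measures ANCOVA with a random subject effect, each of the 10 days being one measurement. Run-in (baseline), QD and TID are the three regimens. For glucose: "When analyzing CGM parameters, the exogenous insulin (basal and bolus insulin amounts) and patient reported carbohydrate intake will be included as covariates". Protocol 8.2 says the same. SAP 2.8.3 applies this model throughout: "All of the CGM parameters will be analyzed for each of the time periods (24-hour, daytime and nighttime) using the Repeated Measures Analysis".

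**The reported estimates.** For this model SAP 2.8.1 names regimen least squares means and changes from baseline. The sentence on intervals and between-regimen changes, "Least squares mean, standard error and 95% confidence intervals will be presented for each treatment regimen and changes between treatment regimens", stands in SAP 2.8.2 and covers insulin only. Unadjusted CGM output is planned as group summaries, with 95% CIs where appropriate (SAP 2.1), tables (4.1) and observed-value figures (4.3). SAP 2.10 plans no other analyses. The table shells are in a separate file (4.5) that was not available.

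**The concern.** If one regimen lets subjects inject less insulin, its net effect on glucose is the direct effect of the capsules plus the consequence of the smaller injections. The endpoint names both. A model that conditions on injected insulin reports only the first, as if every subject had injected the same amount.

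It may not recover even that. If subjects correct high glucose with bolus insulin on the same day, high glucose and high bolus occur together for reasons unrelated to regimen. The fitted insulin slope is then distorted, and the distortion passes into the regimen contrast.

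The study has no power calculation and no stated success rule, so the estimate and its interval are the result. If they answer a different question, a reader could take a difference at equal insulin for the net difference, or miss a net difference that exists.

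**Working it through.** The plan gives no effect size, SD or expected insulin difference, so there is no figure of its own to reproduce.

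**Step 1: are the covariates post-randomization?** Yes. The unit is the day, the diary covers the CGM window, and run-in is itself a level of the regimen factor, so run-in insulin is not a natural reading of the covariate. Same-day alignment is inferred from the daily unit; the SAP does not state it.

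**Step 2: assumed model.** Contrasts are TID minus QD. All inputs are assumptions:
- d: direct effect on glucose (mg/dL).
- t: difference in injected insulin (U), half basal and half bolus, so t_bol = t/2.
- b = 2 mg/dL fall per U.
- r = 0.1 or 0.2 U of same-day corrective bolus per mg/dL.
- s = 10, 15 or 25 mg/dL: SD of daily glucose shocks.
- u = 3 or 6 U: SD of insulin noise, split as u/2 basal and 0.866u bolus.
- No regimen effect on carbohydrate.

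**Step 3: formulas.**
- True joint effect = d − b·t.
- Planned model (separate basal and bolus covariates) = d − k·t_bol, where k = r·s² / (r²·s² + 0.75·u²).
- Without corrective dosing, k = 0 and the planned model returns d.

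**Step 4: results.** Worked cell: s=10, u=3, r=0.1 gives k = 10/(1 + 6.75) = 1.29. Case 1 is then −8 − 1.29·(−2) = −5.42.

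| s | u | r | k | Case 1: d=−8, t=−4, true 0 | Case 2: d=−5, t=−4, true +3 | Case 3: d=−10, t=−2, true −6 |
|---|---|---|---|---|---|---|
| 10 | 3 | 0.1 | 1.29 | −5.42 | −2.42 | −8.71 |
| 10 | 3 | 0.2 | 1.86 | −4.28 | −1.28 | −8.14 |
| 10 | 6 | 0.1 | 0.36 | −7.29 | −4.29 | −9.64 |
| 10 | 6 | 0.2 | 0.65 | −6.71 | −3.71 | −9.35 |
| 15 | 3 | 0.1 | 2.50 | −3.00 | 0.00 | −7.50 |
| 15 | 3 | 0.2 | 2.86 | −2.29 | +0.71 | −7.14 |
| 15 | 6 | 0.1 | 0.77 | −6.46 | −3.46 | −9.23 |
| 15 | 6 | 0.2 | 1.25 | −5.50 | −2.50 | −8.75 |
| 25 | 3 | 0.1 | 4.81 | +1.62 | +4.62 | −5.19 |
| 25 | 3 | 0.2 | 3.94 | −0.13 | +2.87 | −6.06 |
| 25 | 6 | 0.1 | 1.88 | −4.24 | −1.24 | −8.12 |
| 25 | 6 | 0.2 | 2.40 | −3.19 | −0.19 | −7.60 |

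- Case 1: 11 of 12 cells are off by at least 1 mg/dL.
- Case 2: the sign is wrong in 8 of 12, one of them by only −0.2.
- Case 3: 10 of 12 are off by at least 1, with no sign reversal.
- r = 0: the planned model returns −8, −5 and −10.
- t = 0: the gap is zero.

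With one total-insulin covariate instead, k′ = r·s²/(r²·s² + u²) runs from 0.27 to 4.10 and the planned contrast is d − k′·t. The ranges are −6.9 to +8.4, −3.9 to +11.4 and −9.5 to −1.8.

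**Step 5: simulation check.** With 26 subjects, three regimens and 10 days each, 300 replicates of subject-centred least squares gave −7.17 to +1.61 for case 1 with the insulin covariates and −0.13 to +0.15 without them. A REML random-intercept fit (40 replicates per cell) gave −7.4 to +1.0 with them and −0.35 to +0.38 without.

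**The case against.** **The wording can be read another way.** The endpoint could mean two separate influences on glucose, regimen and insulin, and a model with terms for both would fit that. The symmetric pair of models, repeated in both documents, looks deliberate. This stands as a possible reading. Even so, the joint effect that the sentence most directly describes would not be estimated anywhere.

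**The figures rest on chosen inputs.** This stands. The cell counts are not likelihoods, and cases 1 and 2 were set so that the insulin change offsets or outweighs the direct effect. Both regimens total 24 mg a day, and the documents give no reason to expect a particular insulin difference. Biases can also cancel: with s=15, u=3, r=0.1, b=2 and a single insulin covariate, k′ = 22.5/(2.25 + 9) = 2.0 = b. Simulated planned contrasts at those values, with insulin 5 U lower on QD (QD minus TID), were −0.1 against a true 0 and +9.7 against a true +10. At r = 0.2 the result was +12.1 against +10. What follows is that neither the size nor the direction of the gap is known in advance, so a reader cannot correct for it.

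**Unadjusted output is planned, and the unseen shells may hold more.** Group summaries and figures exist, but none is specified as a within-subject QD-TID contrast with an interval. The plan text should not rely on a shell to define a primary estimate.

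**Not every CGM parameter carries the phrase.** Correct. It attaches to mean glucose and, through objective 2, to glycemic variability. Applying the change to the remaining CGM parameters is for consistency.

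**Conclusion.** The concern holds. The target in primary endpoint 2 includes the insulin adjustments, and the only model planned for it conditions on them. That mismatch follows from the text alone and needs no assumed values.

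Its numerical consequence does need them. The gap is zero if injected insulin does not differ between regimens, and it can vanish by cancellation. Otherwise it reached 7.3 mg/dL in case 1 with corrective dosing (8 mg/dL without it), and it reversed the sign of a true +3 mg/dL effect in most case 2 cells.

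This should be fixed before the analysis. It does not invalidate a decision rule, because none is attached to this model. It affects what the primary glucose comparison estimates and how it will be read.

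**What to change.** In SAP 2.8.1 and 2.8.3, and in Protocol 8.2 at the next amendment:

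1. Take the primary QD-TID contrast for mean 24-hour glucose, and for the other CGM parameters, from a model with regimen, random subject and crossover design terms, and no concurrent insulin covariates.
2. Use run-in values as covariates only if run-in is not also a modelled regimen.
3. Carbohydrate may stay, but it too is measured after randomization. Under the assumed model its net slope is 0.15 − 2·0.05 = 0.05 mg/dL per g, so a 20 g regimen difference would shift the contrast by about 1 mg/dL.
4. Report the contrast with a 95% CI beside the insulin contrast, so that net glucose and insulin use are read together.
5. Keep the planned insulin-adjusted model as a supportive analysis, labelled as the difference at equal insulin.
6. For endpoint 1, only add an insulin contrast without concurrent CGM covariates beside the planned model. Insulin requirements may legitimately mean insulin at equal glucose, and no bias is quantified for that model here.

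**Cost.** One added model run per endpoint and a short text change; no new data. Changing Protocol 8.2 needs IRB approval before implementation (Protocol 10). Precision may move either way. In the assumed settings, dropping the insulin covariates while keeping carbohydrate changed the SE of the contrast from 13% lower to 23% higher with corrective dosing, and from 14% lower to 29% higher without it. As a guide, the 95% half-width for a paired difference is t(0.975, n−2)/√n times its SD: about 0.42 SD at n=24 and 0.40 SD at n=26. At assumed SDs of 10, 20 and 30 mg/dL that is about 4, 8 and 12 to 13 mg/dL.
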